13.2 Solicited Local and Systemic Adverse Events

For details please refer to [section 7.1.1 of the protocol](#).

Only solicited local and systemic adverse events reported in the diary card will be analyzed. Implausible measurements will not be taken into consideration in the analysis but listed in the Appendix.

Solicited adverse events will be reported at 30 minutes, at approximately 6 hours post-vaccination on day 1 and then daily until day 7 using structured diaries. The analyses of solicited adverse events will be done separately for 30 minutes and based on three intervals: 6h - day 3, day 4 - 7 and 6h - day 7, each without 30 minutes data. In addition solicited adverse events ongoing after day 7 will be presented as unsolicited AEs.

For erythema, induration and swelling recorded originally as diameters (mm), the following categorization will be used to summarize the data:

Grade 0 (< 25 mm), any (25-50 mm, 51-100 mm, >100 mm)

Body temperature will be broken down by route of measurement according to the recommendations of the Brighton collaboration and will be summarized according to the 3 schemes described below:

- by 0.5 °C increments: <36.0, ≥36.0-<36.5, ≥36.5-<37.0, ≥37.0-<37.5, ≥37.5-<38.0, ≥38.0-<38.5, ≥38.5-<39.0, ≥39.0-<39.5, ≥39.5-<40.0, ≥40.0°C
- by 1.0 °C increments: <36.0, ≥36.0-<37.0, ≥37.0-<38.0, ≥ 38.0-<39.0, ≥39.0-<40, ≥40°C
- <38.0, ≥38.0 °C

Fever, defined as a body temperature of ≥38°C irrespective of route of measurement, will be integrated to the summaries as an indicator of a systemic adverse event.

The analyses will encompass summaries of the data on five levels:

1. Daily reports of subjects with solicited adverse events.
2. Time of first onset of solicited adverse events (excluding 30 min measurement).
3. Solicited adverse events, maximum event severity by event and interval (6h - day 3, day 4 -7, and 6h - day 7, each without 30 min).
4. Duration of solicited adverse events.
5. Solicited adverse events and indicators of solicited adverse events, occurrence of at least one event by category (local, systemic) and interval (6h-Day 3, Day 4-7 and 6h-Day 7, each without 30 min).

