13.3 Unsolicited Adverse Events

The analysis will use unsolicited adverse event data from all reporting sources combined.

All the unsolicited AEs occurring during the study, judged either as probably related, possibly related, or not related to vaccination by the investigator, will be recorded. The original verbatim terms used by investigators to identify AEs in the CRFs will be mapped to preferred terms using the MedDRA dictionary. The unsolicited AEs will then be grouped by MedDRA preferred terms into frequency tables according to SOC.

All AEs will be summarized by vaccine group, according to SOC and PT within SOC. When an unsolicited AE occurs more than once for a subject, the maximal severity and strongest relationship to the vaccine group will be counted.

Only vaccine-emergent AEs will be analyzed, i.e., excluding those after a subject has given informed consent but before vaccination. The selection of unsolicited adverse events and the assignment to time intervals will be done by day of onset and not by days ongoing/persisting.

The summaries will be presented by period of onset and will include frequency distributions of the different adverse events:

- Vaccination 1 AEs, Onset between day 1 and day 28.
- Vaccination 2 AEs, Onset between day 29 and day 57.
- After either vaccination, Onset between day 1 and day 57
- Onset after day 57 through study end.
- At any time during the study, Onset after vaccination 1 on day 1

The analysis of unsolicited adverse events comprises the following categories:

- Any unsolicited adverse event.
- Possibly or probably related unsolicited adverse events.
- Unsolicited adverse events leading to death.

- Serious adverse events.
- Possibly or probably related serious adverse event.
- Unsolicited adverse events leading to premature withdrawal from study.
- Unsolicited adverse events leading to dose reduction, interruption or delay in study vaccination.
- Unsolicited adverse events leading to hospitalization.
- Unsolicited adverse events leading to new onset of chronic disease.
- Unsolicited adverse events of special interest.
- Medically attended adverse events.

Solicited adverse events continuing beyond day 7 will be coded by MedDRA and combined with the respective unsolicited adverse events.

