13.4 Combined Solicited and Unsolicited Adverse Events

A summary of subjects with all combined solicited (regardless of their duration) and unsolicited adverse events will be provided. Solicited adverse events will be coded by MedDRA. For clintrial.gov posting purposes, a summary of combined solicited and unsolicited non-serious adverse events will be produced. A further differentiation of combined adverse events according to seriousness, severity, or relationship is not possible.

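### As SAP Section 13.3 is worded, a solicited reaction that ends by Day 7 but leads to hospitalization, withdrawal or a vaccination delay falls outside those tables, and its place in the serious and medically attended tables is ambiguous

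*SAP*

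**What the plan says.** The references are to the latest SAP version in the file; the earlier versions carry the same Day 7 sentence.

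Section 13.2 analyses solicited reactions from the diary card only: by day, first onset, maximum severity, number of days and occurrence. It then adds: "In addition solicited adverse events ongoing after day 7 will be presented as unsolicited AEs". Section 13.3 repeats the rule: "Solicited adverse events continuing beyond day 7 will be coded by MedDRA and combined with the respective unsolicited adverse events".

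The source of the Section 13.3 tables is given as follows: "The analysis will use unsolicited adverse event data from all reporting sources combined". The list of tables opens with "The analysis of unsolicited adverse events comprises the following categories" and names eleven categories. One is "Unsolicited adverse events leading to hospitalization"; premature withdrawal and dose reduction, interruption or delay carry the same limiting word. Others do not, for example "Serious adverse events".

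Section 13.4 combines solicited reactions of any duration with unsolicited events. For registry posting, "a summary of combined solicited and unsolicited non-serious adverse events will be produced". The next sentence reads: "A further differentiation of combined adverse events according to seriousness, severity, or relationship is not possible".

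**The concern.** Duration is a poor criterion for deciding whether a reaction belongs in an outcome table. Whether an event led to admission, to leaving the study or to a delayed second vaccination has nothing to do with whether it was still present on Day 8. The 7-day diary is aimed at early reactions, and many of these can be expected to end within the diary period.

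This is a first-in-human, dosage-escalation study with adjuvanted arms (Section 1). Its primary safety objective is the comparison with placebo (Section 2.1), and each arm has about 24 subjects (Table 4.1). In arms of that size a single event changes how a hospitalization or withdrawal table reads. A programmer who implements the category names literally would drop such an event without anyone having decided that it should be dropped.

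**Working it through.** The SAP states no figure on this point, so there is none to reproduce. The check sets the sections side by side and traces two hypothetical reactions through them.

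**Step 1: routes into the unsolicited tables.** Sections 13.2 and 13.3 each give one route, continuing beyond Day 7. Neither gives a route based on seriousness, hospitalization, withdrawal, vaccination delay or medical attendance. The worked example in Table 13.2-3 fits this: unsolicited reports are mentioned only for the two reactions that continue to Day 12 and Day 8.

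**Step 2: where outcome tables exist.** The introduction to Section 13 lists exposure, solicited events, unsolicited events and laboratory data. There is no separate section for serious events. The outcome tables appear only in Section 13.3.

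**Step 3: category names in Section 13.3.** Of eleven categories, eight contain the word unsolicited and 11 − 8 = 3 do not. The three are serious events, related serious events and medically attended events. Hospitalization, premature withdrawal, and dose reduction, interruption or delay are among the eight.

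**Step 4: trace.** Reaction A is a mild ache lasting eight days. Reaction B is a fever that leads to admission on Day 2 and resolves on Day 5.

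| Output | Reaction A | Reaction B |
|---|---|---|
| 13.2 solicited tables | counted | counted, with no outcome attribute |
| 13.3 any unsolicited event | enters by the duration rule | no stated route |
| 13.3 hospitalization | outcome absent | outside, by the category name |
| 13.3 withdrawal; dose reduction, interruption or delay | outcome absent | outside by the category name, if it had that outcome |
| 13.3 serious, related serious, medically attended | outcome absent | unclear: heading and source say unsolicited, names do not |
| 13.4 combined summary | counted | counted, with no stated split showing the outcome |

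**Step 5: can 13.2 or 13.4 make up for it?** Section 13.2 has no output by seriousness, hospitalization, withdrawal or medical attendance. Section 13.4 counts the reaction but rules out a split by seriousness, directly after planning a non-serious summary that needs one.

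**Step 6: illustrative size.** Input: n = 24 per arm (Table 4.1). The single event is an assumption, since the SAP gives no event rate.

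- Event counted: 1/24 = 4.2%. Clopper-Pearson 95% lower limit: 1 − 0.975^(1/24) = 0.1%. The upper limit solves (1 − p)^24 + 24p(1 − p)^23 = 0.025, which gives 21.1%.
- Event omitted: 0/24 = 0%. Upper limit: 1 − 0.025^(1/24) = 14.2%.

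**The case against.** The strongest reply is that the Day 7 sentence adds events and excludes none. It does not say that a short reaction recorded on an adverse event form is dropped. Section 13.3 uses all reporting sources and says that all adverse events are summarized by vaccine group. Footnote o to Table 3-1 collects serious events, medically attended events (within a stated 28-day window) and events leading to withdrawal, without separating solicited from unsolicited. Whether a serious solicited reaction is also recorded as an adverse event is something the protocol, which is not shown, may settle.

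For the serious, related serious and medically attended tables this reply stands. A reader might infer that a short serious reaction has no such table at all. The documents do not support that: the three category names carry no limit, so inclusion is unspecified and not ruled out.

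For the other three tables the reply does not suffice. Their names contain the limit, and a protocol rule on recording would not change a selection rule written in the SAP.

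On Section 13.4, the word 'further' can be read as beyond the split just named, so the two sentences are not a necessary contradiction. They still need reconciling, because seriousness is both used and declared unavailable. A reader might also infer that an early hospitalized reaction would be posted as non-serious. Nothing in the text says so: that summary is defined as non-serious.

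**Conclusion.** The point holds in a limited form. As written, a solicited reaction that ends by Day 7 is outside the hospitalization, premature withdrawal, and dose reduction, interruption or delay tables even when it has that outcome. Its inclusion in the serious, related serious and medically attended tables is ambiguous. Section 13.4 does not fill the gap, and its statement on seriousness does not sit well with its own non-serious summary.

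This rests on reading the category names literally and on the SAP alone. The effect on results cannot be sized; the contrast of 1/24 with 0/24 shows only what one event would do in one arm. It might also be inferred that the omission favours the more reactogenic arms, but the SAP contains no figure that would support this. The reactions themselves are not lost, since Section 13.2 reports them by severity and arm. What is missing is their outcome.

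This is more than an absent detail, because a stated duration rule and stated category names would together produce incomplete safety tables. It should be corrected.

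**What to change.** In Section 13.3, add a sentence along these lines: *The tables of serious, related serious, hospitalization, premature withdrawal, dose reduction, interruption or delay, and medically attended adverse events count all such events, solicited or unsolicited, regardless of duration.* Delete the word 'Unsolicited' from the three category names that carry it in this group. The Day 7 rule can stay for the general unsolicited tables.

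In Section 13.4, either remove seriousness from the list of splits that are not possible, or say how the non-serious summary identifies serious events and limit the statement to splits beyond that one.

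The cost is SAP wording and a changed selection condition in the table programs. Footnote o to Table 3-1 already provides for collecting serious events, medically attended events and events leading to withdrawal, so new data collection should not be needed. Whether short solicited reactions with these outcomes are recorded as adverse events should be confirmed against the protocol. No clinical rule changes.

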13.4 Combined Solicited and Unsolicited Adverse Events

A summary of subjects with all combined solicited (regardless of their duration) and unsolicited adverse events will be provided. Solicited adverse events will be coded by MedDRA. For clintrial.gov posting purposes, a summary of combined solicited and unsolicited non-serious adverse events will be produced. A further differentiation of combined adverse events according to seriousness, severity, or relationship is not possible.

13.5 Clinical Safety Laboratory Investigations

Clinical safety laboratory values, and change-from-baseline values (study day 8, 29, 36 and 57 vs. day 1), will be summarized (mean, standard deviation, median, minimum and maximum) at each time-point of assessment, by vaccine group, for subjects in the Overall Safety Set with available laboratory data.

The frequencies of subjects with clinical laboratory values below, within, or above normal ranges will be tabulated for each clinical laboratory variable by vaccine-group and time-point of assessment (3 x 3 shift tables).

The percentages of subjects that show a 'range change abnormal high' (RCAH) or a 'range change abnormal low' (RCAL) are to be tabulated for each clinical laboratory variable by vaccine-group and time point of assessment. A RCAH is a laboratory value that is low or normal at baseline but high post-baseline. A RCAL is a laboratory value that is normal or high at baseline but low post-baseline.

Laboratory values will also be classified and tabulated according to CBER toxicity criteria (CBER 2007b, see section 19 for reference).

Laboratory values that are outside the normal range will also be flagged in the data listings, along with corresponding normal ranges and assessment of clinical significance.

For subjects presenting at least one clinically significant value, an additional listing will be provided of all laboratory results by vaccine group, by subject, and by relevant parameter. Clinical significance assessed by the investigator will be presented.

13.6 Concomitant Medication

The frequencies and percentages of subjects reporting concomitant medications will be tabulated overall and by vaccine group. Medications (generic drug name) will be coded using the WHODRUG dictionary.

14. INTERIM ANALYSIS

14.1 Interim Analysis

An Interim Analysis will not be performed

14.1.1 Futility Analysis

Not Applicable.

15. DATA MONITORING COMMITTEES

A Data Monitoring Committee (DMC) will be implemented to review safety data during scheduled periodic reviews. The DMC will review safety data, as described in the DMC charter.

With regards to timing, DMC meetings are planned:

- Soon after the first 12 subjects in each cohort receive the first vaccine dose, before proceeding with enrollment and vaccination of the remaining subjects in each cohort;
- After the two-vaccination series in each cohort has been completed and before proceeding with enrollment for the subsequent cohort.

DMC review

Decision

Cohort 1: Day 8 for 12 subjects

Complete enrollment in Cohort 1

Cohort 1: Day 57 for all subjects

Begin enrollment in Cohort 2

Cohort 2: Day 8 for 12 subjects

Complete enrollment in Cohort 2

Cohort 2: Day 57 for all subjects

Begin enrollment in Cohort 3

Cohort 3: Day 8 for 12 subjects

Complete enrollment in Cohort 3

Optional review to be determined

16. PEER REVIEW

The type of peer review required for each output is to be identified by the study Biostatistician and Statistical Programmer (SP) in the TOC (see BCDM-14 TEMP 04). Analyses/Outputs requiring statistical peer review correspond usually to the analyses of the primary and secondary objectives, and data conversion programs. Peer review of these analyses should be performed in accordance with the applicable procedures for validation of SAS programs used in clinical data analysis.

The following analyses are identified as key analyses to be peer reviewed by a biostatistician independent from the study:

- Primary immunogenicity analysis.
- Primary safety analysis

The following programs are identified as key programs to be peer reviewed by a second SP:

- Exclusion file(s).
- Data conversion program.
- Primary and secondary immunogenicity analyses
- Safety analyses

17. LIST OF FINAL REPORT TABLES, LISTINGS AND FIGURES

For the complete list of tables, figures, and listings (TFLs), please refer to the Table of Contents (TOC) stored in 'Cabinets/C.A.R.S./Clinical R&D/RSV SUBUNIT (V122)/Studies/001 (205219) V122_01/11 Statistics/11.01 Statistics Oversight/11.01.01 Statistical Analysis Plan '.

18. LAYOUT SPECIFICATIONS FOR TABLES, LISTINGS AND FIGURES

All TFLs are to include the following header:

GlaxoSmithKline Biologicals	Vaccine: RSV F Subunit (RSV101)
Final Report: Study V122_01	Two Doses in Healthy Adults

In all tables, listings and figures, vaccine groups will be labeled as follows:

Group 1A will be labeled as ‘RSV F 45 No Adj’

Group 1B will be labeled as ‘RSV F 45 Alum’

Group 1C will be labeled as ‘RSV F 45 MF59’

Group 1D will be labeled as ‘Placebo’

Group 2A will be labeled as ‘RSV F 90 No Adj’

Group 2B will be labeled as ‘RSV F 90 Alum’

Group 2C will be labeled as ‘RSV F 90 MF59’

Group 2D will be labeled as ‘Placebo’

Group 3A will be labeled as ‘RSV F 135 No Adj’

Group 3B will be labeled as ‘RSV F 135 Alum’

Group 3C will be labeled as ‘RSV F 135 MF59’

Group 3D will be labeled as ‘Placebo’

For the mock-up catalogue to be used during programming, please refer to the document stored in ‘PPD [REDACTED]’, within the SAS Drug Development (SDD) server.

Since all TFLs will be produced using SAS[®], the output actually generated may slightly differ from the mock-ups presented in the study specific Mock-up catalogue.

